**APPENDIX 2      CLINICAL LABORATORY TESTS**

- The tests detailed in [Table A2-1](#) will be performed by the local laboratory.
- Protocol-specific requirements for inclusion or exclusion of participants are detailed in [Section 5.1](#) and [Section 5.2](#) of the protocol.
- Additional tests may be performed at any time during the study as determined necessary by the investigator or required by local regulations.
- Pregnancy Testing: Refer to [Section 5.1](#) for screening criteria, [Appendix 4](#) for women of childbearing potential (WOCBP) criteria, and SoA ([Section 1.3](#)) for timepoints.
- The results of each test must be entered into the electronic Case Report Form (eCRF).
- Investigators must document their review of each laboratory safety report.

### APPENDIX 3      **ADVERSE EVENTS: DEFINITIONS AND PROCEDURES FOR RECORDING, EVALUATING, FOLLOW-UP, AND REPORTING**

#### DEFINITION OF ADVERSE EVENT (AE)

Adverse Event (AE) Definition
 
 
• An adverse event (AE) is any untoward medical occurrence in a patient or clinical study participant, temporally associated with the use of study intervention, whether or not considered related to the study intervention.
 
• NOTE: An AE can therefore be any unfavorable and unintended sign (including an abnormal laboratory finding), symptom, or disease (new or exacerbated) temporally associated with the use of study intervention.
 

Events Meeting the AE Definition
 
 
• Any abnormal laboratory test results (hematology, clinical chemistry, or urinalysis) or other safety assessments (eg, electrocardiogram [ECG], radiological scans, vital signs measurements), including those that worsen from baseline, considered clinically significant in the medical and scientific judgment of the investigator (ie, not related to progression of underlying disease).
 
• Exacerbation of a chronic or intermittent pre-existing condition including either an increase in frequency and/or intensity of the condition.
 
• New conditions detected or diagnosed after study intervention administration even though it may have been present before the start of the study.
 
• Signs, symptoms, or the clinical sequelae of a suspected drug-drug interaction.
 
• Signs, symptoms, or the clinical sequelae of a suspected overdose of either study intervention or a concomitant medication. Overdose per se will not be reported as an AE/serious adverse event (SAE) unless it is an intentional overdose taken with possible suicidal/self-harming intent. Such overdoses should be reported regardless of sequelae.
 


Events NOT Meeting the AE Definition
 
 
• Any clinically significant abnormal laboratory findings or other abnormal safety assessments which are associated with the underlying disease, unless judged by the investigator to be more severe than expected for the participant's condition.
 
• The disease/disorder being studied or expected progression, signs, or symptoms of the disease/disorder being studied, unless more severe than expected for the participant's condition.
 
• Medical or surgical procedure (eg, endoscopy, appendectomy): the condition that leads to the procedure is the AE.
 
• Situations in which an untoward medical occurrence did not occur (social and/or convenience admission to a hospital).
 
• Anticipated day-to-day fluctuations of pre-existing disease(s) or condition(s) present or detected at the start of the study that do not worsen.
 

**DEFINITION OF SAE**

If an event is not an AE per definition above, then it cannot be an SAE even if serious conditions are met (eg, hospitalization for signs/symptoms of the disease under study, death due to progression of disease).

A serious adverse event (SAE) is defined as any untoward medical occurrence that, at any dose:
a. Results in death
b. Is life-threatening The term 'life-threatening' in the definition of 'serious' refers to an event in which the participant was at risk of death at the time of the event. It does not refer to an event, which hypothetically might have caused death, if it were more severe.
c. Requires inpatient hospitalization or prolongation of existing hospitalization In general, hospitalization signifies that the participant has been detained (usually involving at least an overnight stay) at the hospital or emergency ward for observation and/or treatment that would not have been appropriate in the physician's office or outpatient setting. Complications that occur during hospitalization are adverse events (AEs). If a complication prolongs hospitalization or fulfills any other serious criteria, the event is serious. When in doubt as to whether "hospitalization" occurred or was necessary, the AE should be considered serious. Hospitalization for elective treatment of a pre-existing condition that did not worsen from baseline is not considered an AE.
d. Results in persistent disability/incapacity 
 
• The term disability means a substantial disruption of a person's ability to conduct normal life functions.
 
• This definition is not intended to include experiences of relatively minor medical significance, such as uncomplicated headache, nausea, vomiting, diarrhea, influenza, and accidental trauma (e.g. sprained ankle), which may interfere with or prevent everyday life functions but do not constitute a substantial disruption.
 

e. Is a congenital anomaly/birth defect
f. Other situations 
 
• Medical or scientific judgment should be exercised in deciding whether SAE reporting is appropriate in other situations such as important medical events that may not be immediately life-threatening or result in death or hospitalization but may jeopardize the participant or may require medical or surgical intervention to prevent one of the other outcomes listed in the above definition. These events should usually be considered serious. Examples of such events include other invasive or malignant cancers, intensive treatment in an emergency room or at home for allergic bronchospasm, blood dyscrasias or convulsions that do not result in hospitalization, or development of drug dependency or drug abuse.
 
• Concurrent elevation of AST or ALT <math>>3 \times</math> ULN AND total bilirubin <math>>2 \times</math> ULN or INR <math>>1.5</math> may indicate severe drug-induced liver injury (possible Hy's law case). All qualifying events must be reported as an SAE.
 

**RECORDING AND FOLLOW-UP OF AE AND/OR SAE**

AE and SAE Recording

 
• When an adverse event (AE)/serious adverse event (SAE) occurs, it is the responsibility of the investigator to review all documentation (eg, hospital progress notes, laboratory reports, and diagnostics reports) related to the event.
 
• The investigator will then record all relevant AE/SAE information in the electronic Case Report Form (eCRF). Additionally, investigative sites should report SAEs within 24 hours of becoming aware of the event to the Chiltern/Covance Pharmacovigilance Department using the paper SAE report form. See section below on the Reporting of SAEs.
 
• It is not acceptable for the investigator to send photocopies of the participant’s medical records to the Sponsor or designee in lieu of completion of the AE/SAE CRF.
 
• There may be instances when copies of medical records for certain cases are requested by the Sponsor or designee. In this case, all participant identifiers, with the exception of the participant number, will be redacted on the copies of the medical records before submission to the Sponsor or designee.
 
• The investigator will attempt to establish a diagnosis of the event based on signs, symptoms, and/or other clinical information. Whenever possible, the diagnosis (not the individual signs/symptoms) will be documented as the AE/SAE.
 

Assessment of Intensity


The investigator will assess intensity (severity) for each AE and SAE reported during the study using the definitions found in the National Cancer Institute Common Terminology Criteria for Adverse Events Version 5 (NCI CTCAE v5) or later. The NCI CTCAE v5 displays Grades 1 through 5 with unique clinical descriptions of severity for each referenced AE. Should a participant experience any AE not listed in the NCI CTCAE v5, the following grading system should be used to assess severity:
 
 
• Grade 1 (Mild) – experiences which are usually transient, requiring no special treatment, and not interfering with the participant’s daily activities
 
• Grade 2 (Moderate) – experiences which introduce some level of inconvenience or concern to the participant, and which may interfere with daily activities, but are usually ameliorated by simple therapeutic measures
 
• Grade 3 (Severe) – experiences which are unacceptable or intolerable, significantly interrupt the participant’s usual daily activity, and require systemic drug therapy or other treatment
 
• Grade 4 (Life-threatening) – experiences which cause the participant to be in danger of life-threatening consequences and urgent intervention is required
 
• Grade 5 (Death) – experiences which result in participant death
 
 
An AE that is assessed as severe should not be confused with a SAE. Severe is a category utilized for rating the intensity of an event; and both AEs and SAEs can be assessed as severe. An event is defined as ‘serious’ when it meets at least 1 of the predefined outcomes as described in the definition of an SAE, not when it is rated as severe.

**Assessment of Causality**

- The investigator is obligated to assess the relationship between both study interventions/study drugs and each occurrence of each AE/SAE.
- A “reasonable possibility” of a relationship conveys that there are facts, evidence, and/or arguments to suggest a causal relationship, rather than a relationship cannot be ruled out.
- The investigator will use clinical judgment to determine the relationship.
- Alternative causes, such as underlying disease(s), concomitant therapy, and other risk factors, as well as the temporal relationship of the event to study intervention administration will be considered and investigated.
- The investigator will also consult the Investigator’s Brochure in his/her assessment.
- For each AE/SAE, the investigator **must** document in the medical notes that he/she has reviewed the AE/SAE and has provided an assessment of causality.
- There may be situations in which an SAE has occurred, and the investigator has minimal information to include in the initial report to the Sponsor or designee. However, **it is very important that the investigator always make an assessment of causality for every event before the initial transmission of the SAE data to the Sponsor or designee.**
- The investigator may change his/her opinion of causality in light of follow-up information and send a SAE follow-up report with the updated causality assessment.
- The causality assessment is one of the criteria used when determining regulatory reporting requirements.

**Follow-up of AEs and SAEs**

- The investigator is obligated to perform or arrange for the conduct of supplemental measurements and/or evaluations as medically indicated or as requested by the Sponsor or designee to elucidate the nature and/or causality of the AE or SAE as fully as possible. This may include additional laboratory tests or investigations, histopathological examinations, or consultation with other health care professionals.
- If a participant dies during participation in the study or during a recognized follow-up period, the investigator will provide the Sponsor or designee with a copy of any post-mortem findings including histopathology.
- New or updated information will be recorded in the originally completed eCRF.
- The investigator will submit any updated SAE data to Covance Pharmacovigilance Department within 24 hours of receipt of the information on an updated SAE report form to either the email or fax listed below.

**REPORTING OF SAES****SAE Reporting to the Sponsor or Designee via Paper CRF**

- Investigative sites should report SAEs within 24 hours of becoming aware of the event to the Chiltern/Covance Pharmacovigilance department using the paper SAE report form and any supporting documentation either by email or fax.  

Email: [contact]  
[contact]
- In rare circumstances and in the absence of email or facsimile equipment, notification by telephone to the Medical Monitor is acceptable with a copy of the SAE report form sent by overnight mail or courier service to Chiltern/Covance CRO Pharmacovigilance Department.
- Contacts for SAE reporting can be found in the Regulatory binder.

## APPENDIX 4 CONTRACEPTIVE GUIDANCE AND COLLECTION OF PREGNANCY INFORMATION

### DEFINITIONS

#### Woman of Childbearing Potential (WOCBP)

A woman is considered fertile following menarche and until becoming postmenopausal unless permanently sterile (see below).

If fertility is unclear (e.g. amenorrhea in adolescents or athletes) and a menstrual cycle cannot be confirmed before first dose of study intervention, additional evaluation should be considered.

Women in the following categories are not considered WOCBP:

1. Premenarchal
2. Premenopausal female with 1 of the following:
  - Documented hysterectomy
  - Documented bilateral salpingectomy
  - Documented bilateral oophorectomy
  - For individuals with permanent infertility due to an alternate medical cause other than the above, (e.g. mullerian agenesis, androgen insensitivity), investigator discretion should be applied to determining study entry.
  - Note: Documentation can come from the site personnel's review of the participant's medical records, medical examination, or medical history interview.
3. Postmenopausal female
  - A postmenopausal state is defined as no menses for 12 months without an alternative medical cause.
  - A high follicle-stimulating hormone (FSH) level in the postmenopausal range may be used to confirm a postmenopausal state in women not using hormonal contraception or hormonal replacement therapy (HRT). However, in the absence of 12 months of amenorrhea, confirmation with more than one FSH measurement is required.
  - Females on HRT and whose menopausal status is in doubt will be required to use one of the non-estrogen hormonal highly effective contraception methods if they wish to continue their HRT during the study. Otherwise, they must discontinue HRT to allow confirmation of postmenopausal status before study enrollment.

**CONTRACEPTION GUIDANCE**

CONTRACEPTIVES a ALLOWED DURING THE STUDY INCLUDE:
Highly Effective Methods b That Have Low User Dependency Failure rate of <1% per year when used consistently and correctly.

 
• Implantable progestogen-only hormone contraception associated with inhibition of ovulation c
 
• Intrauterine device (IUD)
 
• Intrauterine hormone-releasing system (IUS)c
 
• Bilateral tubal occlusion
 

Vasectomized partner (Vasectomized partner is a highly effective contraceptive method provided that the partner is the sole sexual partner of the woman of childbearing potential (WOCBP) and the absence of sperm has been confirmed. If not, an additional highly effective method of contraception should be used. Spermatogenesis cycle is approximately 90 days.)
Highly Effective Methods b That Are User Dependent Failure rate of <1% per year when used consistently and correctly.
Combined (estrogen- and progestogen-containing) hormonal contraception associated with inhibition of ovulation c 
 
• oral
 
• intravaginal
 
• transdermal
 
• injectable
 

Progestogen-only hormone contraception associated with inhibition of ovulation c 
 
• oral
 
• injectable
 

Sexual abstinence (Sexual abstinence is considered a highly effective method only if defined as refraining from heterosexual intercourse during the entire period of risk associated with the study intervention. The reliability of sexual abstinence needs to be evaluated in relation to the duration of the study and the preferred and usual lifestyle of the participant.)

Note: Periodic abstinence (calendar, symptothermal, post-ovulation methods), withdrawal (coitus interruptus), spermicides only, and lactational amenorrhea method are NOT acceptable methods of contraception. Male condom and female condom should not be used together (due to risk of failure with friction).

a Contraceptive use by men or women should be consistent with local regulations regarding the use of contraceptive methods for those participating in clinical studies.

b Failure rate of <1% per year when used consistently and correctly. Typical use failure rates differ from those when used consistently and correctly.

c Hormonal contraception efficacy may potentially be decreased due to interaction with RMC-4630 thus male condoms must be used in addition to hormonal contraception.

## COLLECTION OF PREGNANCY INFORMATION

### Male Participants With Partners Who Become Pregnant

- The investigator will attempt to collect pregnancy information on any male participant's female partner who becomes pregnant while the male participant is in this study. This applies only to male participants who receive RMC-4630 and cobimetinib under this protocol.
- After obtaining the necessary signed informed consent from the pregnant female partner directly, the investigator will record pregnancy information on the appropriate form and submit it to the Sponsor within 24 hours of learning of the partner's pregnancy. The female partner will also be followed to determine the outcome of the pregnancy. Information on the status of the mother and child will be forwarded to the Sponsor. Generally, the follow-up will be no longer than 6 to 8 weeks following the estimated delivery date. Any termination of the pregnancy will be reported regardless of fetal status (presence or absence of anomalies) or indication for the procedure.

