- **Embryo fetal toxicity:** Based on data from animal studies and its mechanism of action, osimertinib can cause fetal harm when administered to a pregnant woman. In animal reproduction studies, osimertinib caused post-implantation fetal loss when administered during early development at a dose exposure 1.5 times the exposure at the recommended clinical dose. When males were treated prior to mating with untreated females, there was an increase in preimplantation embryonic loss at plasma exposures of approximately 0.5 times those observed at the recommended dose of 80 mg once daily. Verify pregnancy status of females of reproductive potential prior to initiating osimertinib. Advise pregnant women of the potential risk to a fetus. Advise females of reproductive potential to use effective contraception during treatment with osimertinib and for 6 weeks after the final dose. Advise males with female partners of reproductive potential to use effective contraception for 4 months after the final dose.

Refer to Tagrisso (osimertinib) US Package Insert for more information

**2.3.1.5. Potential Risks of RMC-4630 and Osimertinib Combination  
(for US Study Only)**

The overlapping toxicities of a SHP2 inhibitor and an EGFR inhibitor have not been formally assessed in non-clinical models. As SHP2 is located downstream of EGFR receptor, both agents inhibit signaling in the RAS-MAPK signaling pathway and it is possible that overlapping toxicities may be observed.

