#### **4.2.4. Duration of Therapy**

Participants will be permitted to remain on-study therapy until disease progression per RECIST v1.1, unacceptable toxicity, or other criteria for withdrawal are met ([Section 7.1](#) and [Section 7.2](#)), or end of study ([Section 4.3](#)), whichever occurs first. Participants will return to the clinical site for an EOT visit within 30 days after last treatment dose. Alternatively, participants may withdraw from the study at any time with or without cause and will be encouraged for EOT evaluation.

After termination of treatment, participants will continue on study for long-term survival follow-up every 3 months ( $\pm 2$  weeks), unless they withdraw consent for further follow-up or end of study.

The anticipated duration of the study is approximately 3 years, including 2 years of enrollment and 1 year of follow-up visits.

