**All participants must meet ALL of the following inclusion criteria:**

1. Age  $\geq 18$  years
2. Evaluable or measurable disease per RECIST v1.1 criteria for Dose-Escalation; measurable disease (only) per RECIST v1.1 for Dose-Expansion
3. Eastern Cooperative Oncology Group (ECOG) performance status of  $\leq 1$  with no deterioration over the previous 2 weeks
4. Adequate hematological and organ function, confirmed by the following laboratory values at local investigative site:
  - Bone Marrow Function
  - Absolute neutrophil count (ANC)  $\geq 1.0 \times 10^9/L$
  - Platelets  $\geq 100 \times 10^9/L$  without transfusion support
  - Hemoglobin  $\geq 9$  gm/dL
  - **Hepatic Function**
    - Aspartate aminotransferase (AST) and alanine aminotransferase (ALT)  $\leq 3 \times$  upper limit of normal (ULN)
    - Bilirubin  $\leq 1.5 \times$  ULN ( $< 3.0$  mg/dL if participant has Gilbert's disease)
  - **Renal Function**
    - Blood creatinine  $\leq 1.5 \times$  ULN or creatinine clearance of  $> 50$  mL/min (using Cockcroft-Gault formula or 24-hour urine collection)
  - **Coagulation**
    - Prothrombin time (PT)/international normalized ratio (INR) and activated partial thromboplastin time or partial thromboplastin time (aPTT/PTT)  $< 1.3 \times$  ULN (or partial thromboplastin time (PTT)) or within therapeutic range if receiving therapeutic anticoagulation that would affect the PT/INR.
5. Capable of giving signed informed consent. Willing and able to comply with study requirements and restrictions.
6. Life expectancy  $\geq 12$  weeks
7. Females of childbearing potential must agree to always use 2 effective forms of contraception during the course of the study and for at least 3 months after completion of study therapy.
8. Males with partners of childbearing potential must agree to always use 2 effective forms of contraception during the course of the study and for at least 3 months after completion of RMC-4630 and cobimetinib or 4 months after completion of RMC-4630 and osimertinib.
9. Negative blood pregnancy test within 14 days of commencement of study medications in women of childbearing potential.

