#### **8.3.5. Pregnancy**

- Details of all pregnancies in female participants and, if indicated, female partners of male participants will be collected after the start of study intervention and until EOT visit.
- If a pregnancy is reported, the investigator should inform the Sponsor within 24 hours of learning of the pregnancy and should follow the procedures outlined in [Appendix 4](#).
- Abnormal pregnancy outcomes (eg, spontaneous abortion, fetal death, stillbirth, congenital anomalies, ectopic pregnancy) are considered SAEs.

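### Appendix 4 leaves osimertinib-arm men out of the partner-pregnancy consent and outcome-follow-up procedure without giving a reason

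*Combined protocol and SAP*

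**What the plan says.** Section 8.3.5 has three bullets that matter here.

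- The first provides that details of pregnancies in female participants and, where indicated, "female partners of male participants will be collected after the start of study intervention and until EOT visit". It names no arm.
- The second governs what happens after any report: "the investigator should inform the Sponsor within 24 hours of learning of the pregnancy and should follow the procedures outlined in". The cross-reference is to Appendix 4. It names no arm and no end date.
- The third classes abnormal pregnancy outcomes as SAEs.

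Appendix 4 then gives the procedure for male participants. The investigator attempts to collect information on a partner who becomes pregnant while the man is in the study. After the partner's own signed consent, the pregnancy is recorded and sent to the sponsor, and she is followed to the outcome, generally no later than 6 to 8 weeks after the estimated delivery date. The scope is limited in one sentence: "This applies only to male participants who receive RMC-4630 and cobimetinib under this protocol". The parallel text for female participants has no arm limit.

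Inclusion criterion 8 in Section 5.1 requires men with partners of childbearing potential to use two forms of contraception during the study and "for at least 3 months after completion of RMC-4630 and cobimetinib or 4 months after completion of RMC-4630 and osimertinib". For osimertinib, Section 2.3.1.4 gives the label advice: "Advise males with female partners of reproductive potential to use effective contraception for 4 months after the final dose". It also reports that when treated males were mated with untreated females, "there was an increase in preimplantation embryonic loss at plasma exposures of approximately 0.5 times those observed at the recommended dose".

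**The concern.** The body of the protocol sends every reported pregnancy to Appendix 4, and Appendix 4 then excludes the men of one arm. Those men have the longer contraception period and take a drug with a reported animal finding after male dosing. They also take RMC-4630, as the other arm does.

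The stake is the fetal-exposure record. Section 8.3.5 treats an abnormal outcome as an SAE, but a site can report an outcome only if it learns of it. Without partner consent and planned follow-up, the sponsor may know that a partner conceived and never know what happened. This affects safety follow-up only.

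**Working it through.** The plan states no figure to reproduce. The check is a comparison of the sections.

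**1. A partner pregnancy traced through the text**

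| Step | Cobimetinib-arm man | Osimertinib-arm man |
|---|---|---|
| Sponsor notified within 24 hours (8.3.5, second bullet) | Yes | Yes |
| Abnormal outcome classed as an SAE (8.3.5, third bullet) | Yes | Yes |
| Partner consent, form and outcome follow-up (Appendix 4) | Yes | Excluded by the scope sentence |
| Contraception after treatment (5.1, criterion 8) | At least 3 months | 4 months |

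The exclusion has no time element, so it applies during treatment as well as after it. The readable text contains no other partner-consent or outcome procedure for the osimertinib arm.

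**2. Is there a stated reason for the exclusion?**

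None is given. RMC-4630 is common to both arms, so a concern about that drug would apply to both. In the readable text, the reproductive finding for cobimetinib (Section 2.3.1.2) comes from dosing pregnant rats. The only readable finding after male dosing is the one for osimertinib in Section 2.3.1.4. The readable evidence therefore gives no ground for covering cobimetinib-arm men and leaving osimertinib-arm men out.

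**3. Size**

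Sections 4.2.2 and 9.2 put the osimertinib arm at 24 participants in total. The documents do not give the number of men, the number with partners of childbearing potential, or an expected number of pregnancies. No count of affected pregnancies can be derived.

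**4. Secondary point: when collection ends**

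- Section 8.3.5, first bullet: routine collection stops at EOT. Section 4.2.4, and likewise 4.1.4: "Participants will return to the clinical site for an EOT visit within 30 days after last treatment dose".
- Appendix 4: the criterion is being in, or participating in, the study. Section 4.2.4 says that after treatment "participants will continue on study for long-term survival follow-up every 3 months", which suggests time beyond EOT. Section 7.1 speaks of removal from the study at, for example, progression, which suggests the opposite, although it also provides long-term follow-up.
- Criteria 7 and 8: contraception runs at least 3 months (women in both arms, cobimetinib-arm men) or 4 months (osimertinib-arm men).

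With a month taken as about 30.4 days, 3 months is about 91 days and 4 months about 122. With EOT on day 30 at the latest, the stretch between EOT and the end of contraception is at least 91 − 30 = 61 days, or 122 − 30 = 92 days. Over that stretch the sections disagree on whether pregnancies are actively collected. These are calendar lengths, not a measure of missed pregnancies.

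**The case against.** The strongest reply on the main point is that Section 8.3.5 covers partners only where indicated. That can be read as leaving Appendix 4 to decide which partners are included, so the two sections need not contradict each other. This stands as far as it goes. It would make the exclusion compatible with Section 8.3.5, but it would not explain it, and criterion 8 and Section 2.3.1.4 point the other way. The criticism is therefore an unexplained exclusion, not a flat contradiction.

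It is also fair to say that the arm is small, that two contraceptive methods are required, and that notification and SAE status survive. All of this limits the size of the point but does not supply the missing procedure.

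On the secondary point, a reader might infer that pregnancies conceived after EOT but within the contraception period go uncollected, and might quote the share of that period as a gap. The documents do not support this. Only the first bullet of Section 8.3.5 ends at EOT. The second has no end date, so a pregnancy reported later still appears notifiable and, for women and cobimetinib-arm men, goes to Appendix 4. The Appendix 4 wording may also include survival follow-up. The Schedule of Activities is redacted, so what is asked at follow-up contacts cannot be checked. The documents contain no requirement that active collection match the contraception period. What remains is an ambiguity about active collection after EOT.

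**Conclusion.** The main point holds on the current text. In the osimertinib arm, a partner pregnancy during or after treatment is notified to the sponsor but has no consent or outcome-follow-up procedure, and the protocol gives no reason. This is a small but real defect in safety follow-up, in an arm planned at 24 participants. It rests on the readable text and assumes that no redacted section supplies a separate procedure for these men.

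The end-of-collection point is secondary and optional. Sections 8.3.5 and Appendix 4 use different end points, and one should be chosen, but no gap in collection is demonstrated. Neither point affects an endpoint, a dose decision or an estimate.

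**What to change.** In Appendix 4, under male participants, replace the scope sentence with: *This applies to male participants who receive RMC-4630 with cobimetinib or with osimertinib.*

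The cost is small. The existing partner consent form and follow-up, to 6 to 8 weeks after the estimated delivery date, would be used in the second arm. Appendix 1 requires IRB approval of the amendment and of consent documents. No visits or participants are added.

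Optionally, state one end date for active collection in Section 8.3.5 and use it in both parts of Appendix 4 in place of the reference to being in the study. The natural choice is the end of the contraception period: 3 months after the last dose, or 4 months for partners of osimertinib-arm men. If collection is to be active, a pregnancy question could be asked at the 3-monthly survival contacts; whether one is already asked there cannot be seen in the redacted schedule.
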